**f) Access to resources if needed as a consequence of the research.**

**State whether you have medical or psychological resources available that participants might require as a consequence of the research when applicable. Please describe these resources.**

The project will have sufficient medical or psychological resources available. There will be neurologists, psychologists, nurses, psychiatrists and educational resources available for all Veterans that are part of this study.

**g) Lead Investigator or Coordinating Institution in Multi-site Study.**

**Please explain (i) your role in coordinating the studies, (ii) procedures for routine communication with other sites, (iii) documentation of routine communications with other sites, (iv) planned management of communication of adverse outcomes, unexpected problems involving risk to participants or others, protocol modifications or interim findings.**

## 1. Purpose

**a) In layperson's language state the purpose of the study in 3-5 sentences.**

Repetitive Transcranial Magnetic Stimulation (rTMS) to Improve Cognitive Function in TBI: The proposed study will evaluate the safety, durability and efficacy of repetitive Transcranial Magnetic Stimulation (rTMS) as a promising non- invasive therapeutic treatment for executive function (EF) deficits and other outcomes (such as: headache, pain, etc) seen in 100 Veterans with mild to moderate Traumatic Brain Injury (TBI).

**b) State what the Investigator(s) hope to learn from the study. Include an assessment of the importance of this new knowledge.**

Many returning OEF/OIF Veterans with concussion histories report cognitive problems that may last for months or even years (Schneiderman et al., 2008; Hoge et al., 2008). Although deployment itself can be associated with cognitive problems (Vasterling et al, 2006), having co-morbid conditions such as post traumatic stress disorder (PTSD) and depression may prolong the symptoms of TBI resulting in lowered attention, processing speed, learning and memory (Nelson et al., 2012; Caeyenberghs et al., 2012). Strong evidence also suggests that a history of TBI increases risk for developing PTSD (Eckart et al., 2011). Significant progress has been made towards understanding the pathophysiology and neuropsychological changes associated with the acute and long term sequelae of TBI, including its complicated relationship with PTSD (Brenner et al., 2011; Hallbauer et al.,

---

**Title :** Repetitive Transcranial Magnetic Stimulation to Improve Cognitive Function in TBI  
**Approval Period:** 12/11/2018 - 02/13/2019

---

2009;  
Villamar et al., 2012). However, few studies have addressed what mechanisms of TBI may be responsive to therapeutic treatment.

The most common cognitive difficulties faced by Veterans with TBI include executive function deficits such as impaired attention, verbal fluency, poor planning, reduced working memory, and mental flexibility (Godefroy et al., 2003). A survey of Army infantry who suffered from TBI reported that 31.4% complained of concentration problems and 24.6% complained of memory problems (Nelson et al., 2012). Numerous studies confirm that Dorso Lateral Prefrontal Cortex (DLPFC) is involved in inhibition, planning and set-switching - key components of executive function (Vanderhasselt et al., 2006). Deficits in executive function following mild TBI (mTBI) are also associated with injury to the axons and involve the DLPFC (Lipton et al., 2009). In fact, patients with focal lesions in this brain region performed significantly worse than controls on the Trail Making Test (TMT: primary outcome measure) suggesting impaired cognitive set-shifting (Yochim et al., 2007). Moreover, control participants performed significantly better on TMT than patients with mTBI (Brooks et al., 1999). We hope to demonstrate improvement of this deficit in Veterans with mild and moderate TBI through rTMS treatment. Additionally we would also report on the efficacy of using functional brain connectivity (thru advanced neuroimaging) as a biomarker to capture this improvement in executive function.

Previous studies have documented the relationship between injury severity, cognitive impairment and functional status (Bush et al., 2003; Senathi-Raja et al., 2010). In fact, Bercaw et al, (2011) reported that neuropsychological performance at year 1 post-injury predicted functional outcomes in year 2. Although reports of mild TBI patients returning to baseline functioning one year post-injury have been documented, 7% to 33% of these patients experience persistent symptoms (Belanger et al., 2005). Note that regardless of injury severity, one of the most frequently reported post-TBI sequelae is cognitive dysfunction (e.g, memory problems and executive function: Terrio et al., 2009; Senathi-Raja et al., 2010). Among these patients

---

**Title :** Repetitive Transcranial Magnetic Stimulation to Improve Cognitive Function in TBI  
**Approval Period:** 12/11/2018 - 02/13/2019

---

there is often little correlation between subjective (e.g, self-report) and objective markers (eg, neuropsychological test performance) of such dysfunction (Brenner et al., 2011). Moreover these cognitive complaints have been associated with poorer psychosocial functioning (eg, return to work; Benedictus et al., 2010).

**Specific Aims are:**

To assess the efficacy and durability of benefits of repetitive Transcranial Magnetic Stimulation (rTMS) as a promising non-invasive therapeutic treatment for executive function deficits seen in Veterans with mild to moderate TBI.

**Primary Hypothesis:**

Veterans with mild to moderate TBI receiving active rTMS treatment will show improvement of > 1 SD on performance between baseline and post-treatment on any one of the following: the Trail Making Test part B, D-KEFS Verbal Fluency and/or D-KEFS Color-Word Interference Test) than Veterans receiving sham rTMS.

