**Secondary Hypotheses:**

1. Sustained Improvement. At the end of the 6-month post treatment follow-up, TBI patients who received rTMS would be more likely to continue to have reduced symptoms, i.e. greater "executive function improvement" than patients who received sham rTMS.
2. Secondary consequences of TBI will improve with rTMS treatment, i.e. scores on Quality of Life (QOL) scale will show significantly greater improvement in patients with mild to moderate TBI who received rTMS treatment.
3. Moderators of Response. Age, severity of symptoms at baseline, type of comorbidity (PTSD, time since injury, sleep, depression substance abuse, medication use, cognitive exercises, fatigue or any combinations of these), TBI type, duration of

**Title :** Repetitive Transcranial Magnetic Stimulation to Improve Cognitive Function in TBI  
**Approval Period:** 12/11/2018 - 02/13/2019

illness and prior treatment resistance (rTMS/ECT): may affect or "moderate" treatment response.

4. Greater functional connectivity will be observed in hub centers of the Default Mode Network (DMN), particularly the precuneus/posterior cingulate area as measured by resting state fMRI at follow-up compared to baseline in those TBI patients treated with rTMS compared to those treated with sham.

5. Mediators of Response to Treatment: to establish a preliminary understanding of the underlying mechanisms related to rTMS modulation of synaptic repair in TBI we will also look at Brain Derived Neurotrophic Factor (BDNF) plasma samples in our population.

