- Interviews, Self-Report Questionnaires (same as above);
- Pure Tone Audiometry;
- Cognitive testing including executive function main

outcome measure and webneuro computerized testing

• Neuroimaging: Diffusion Tensor Imaging (DTI), Functional MRI (fMRI), structural MRI

• Blood samples (60 cc) will be taken for processing of BDNF from blood plasma.

- b) Explain how the above research procedures are the least risky that can be performed consistent with sound research design.**

The study design involves minimal risk to participants. This research project is a placebo control study design.

- c) State if deception will be used. If so, provide the rationale and describe debriefing procedures. Since you will not be fully informing the participant in your consent process and form, complete an alteration of consent (in section 13). Submit a debriefing script (in section 16).**

Deception will not be used.

- d) State if audio or video recording will occur. Describe what will become of the recording after use, e.g., shown at scientific meetings, erased. Describe the final disposition of the recordings.**

None will occur.

- e) Describe alternative procedures or courses of treatment, if any, that might be advantageous to the participant. Describe potential risks and benefits associated with these. Any standard treatment that is being withheld must be disclosed in the consent process and form. (i.e. standard-of-care drug, different interventional procedure, no procedure or treatment, palliative care, other research studies).**

There are many alternative procedures/courses of improving executive function including cognitive training, weight loss, exercise, etc although their clinical feasibility can be questioned. No standard treatments for improving executive function are being withheld from potential participants in this study.

- f) Will it be possible to continue the more (most) appropriate therapy for the participant(s) after the conclusion of the study?**

If rTMS is found to be effective for improving cognitive function, it may be possible to have patients return for booster sessions.

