### 3. Background

#### a) Describe past experimental and/or clinical findings leading to the formulation of the study.

Overview of rTMS in Cognitive Dysfunction in mild and Moderate TBI  
 Repetitive TMS is a method of delivering therapeutic, non-invasive brain stimulation. While not yet utilized in TBI research on a large scale, rTMS is well suited for this pilot project given the clinical and research expertise in rTMS trials for various other common Veteran complaints (e.g., team of 5 MD's, 1 RN, 3 clinical neuropsychologists and 2 neuroimaging researchers in the VA). rTMS is currently being used at the VA Palo Alto and Stanford University in the treatment of: pain (VA Rehabilitation grant funded: PI: [name] & Co-I/Co-Protocol Director: [name]), depression (VA Co-op studies funded, PI: [name]; Co-op studies funded, PI: [name]), and PTSD (NIH funded project: [name]). At present it is an FDA-approved for treatment for major depression (Oreardon et al., 2007; George et al., 2010; [name], current consultant). A recent VA study reported improvements in PTSD and related symptoms in Veterans with PTSD who received rTMS (Watts et al., 2012). Also of relevance in our TBI Veterans, a major industry trial of rTMS in Treatment Refractory Major Depression (TRMD) has been completed. This randomized controlled trial involved 301 medication-free patients with TRMD and excluded patients dual-diagnosed with co-morbid substance abuse (past year) or PTSD. Response and remission rates were significantly better in rTMS than in controls at the end of 6 weeks treatment, but results were smaller and not

---

**Title :** Repetitive Transcranial Magnetic Stimulation to Improve Cognitive Function in TBI  
**Approval Period:** 12/11/2018 - 02/13/2019

---

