## 8. Participant Population

- a) **State the following: (i) the number of participants expected to be enrolled at Stanford-affiliated site(s); (ii) the total number of participants expected to enroll at all sites; (iii) the type of participants (i.e. students, patients with certain cancer, patients with certain cardiac condition) and the reasons for using such participants.**

(i) 100 participants are expected to be enrolled  
(ii) 100 participants at VAPAHCS  
(iii) all participants will be Veterans, Military personnel and Civilians.

- b) **State the age range, gender, and ethnic background of the participant population being recruited.**

Age range: 20-65 years  
Note: We may include participants between 65-70 if they contact us and pass the screening (and are not showing cognitive decline related to dementia)  
Gender: Males and Females  
Ethnic Background: Any race or ethnic origin

- c) **State the number and rationale for involvement of potentially vulnerable subjects in the study (including children, pregnant women, economically and educationally disadvantaged, decisionally impaired, homeless people, employees and students). Specify the measures being taken to minimize the risks and the chance of harm to the potentially vulnerable subjects and the additional safeguards that have been included in the protocol to protect their rights and welfare.**

Children, pregnant women, economically and educationally disadvantaged, decisionally impaired, and homeless people will not be recruited for this protocol.

- d) **If women, minorities, or children are not included, a clear compelling rationale must be provided (e.g., disease does not occur in children, drug or device would interfere with normal growth and development, etc.).**

There will be no participation of children in this study.

- e) **State the number, if any, of participants who are laboratory personnel, employees, and/or students. They should render the same written informed consent. If payment is allowed, they should also receive it. Please see Stanford University policy.**

It is unlikely that any laboratory personnel, employees, or students will qualify for participation in this study. If any do qualify and wish to participate, they will be treated the same as any other participant.

**Title :** Repetitive Transcranial Magnetic Stimulation to Improve Cognitive Function in TBI  
**Approval Period:** 12/11/2018 - 02/13/2019

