is the most common delayed sequelae of TBI. But this incidence is very low (about 5%) in TBI patients with closed head injury (Ropper et al., 2005) who are most likely our mild and moderate TBI patients. In a clinical setting, for example in Polytrauma Transitional Rehabilitation Program (PTRP – VAPA) the expected recovery trajectory for persons with mTBI is full cognitive recovery in 3-6 months following injury. Persisting or worsening cognitive status is often related to other co-morbid psychiatric issues, such as depression and PTSD, chronic pain, sleep apnea (all will be) used as covariates in our analysis). Including persons with moderate TBI in our study would likely allow for examination of rehabilitation treatment effects on cognitive functioning for those who tend to have persisting cognitive difficulties following injury. On PTRP, patients are often admitted from the acute inpatient rehab unit on anticonvulsant medications if they had a seizure 1 day or more following the injury. Typically, if the patient experienced a seizure immediately at the scene of the incident, they are not considered at a greater risk for subsequent seizures. For those who do not have a history of seizures following injury, they are not considered at a greater risk of subsequent seizures and are not placed on anticonvulsant medications. Importantly, the interval between the head injury and the first seizure varies greatly (Demirtas-Tatlidede et al., 2012) and must be considered as a variable for recruitment in this study. Currently PTRP houses patients 2 months to 2 years post TBI. Note, that there is only one case study which performed detailed safety assessments and reported a lack of adverse events in a patient with severe TBI following application of a specific rTMS protocol over 5 consecutive days through 6 weeks (Pape et al., 2009). Our protocol will be highly stringent and will exclude any severe TBI patients (including those with any fractures, metal plates or open head injuries), acute patients or those who have had a concussion within the last 2 months, and those who have a history of seizures of any type.

Neuropsychology testing - The risks posed by neuropsychological testing are mild frustration and mild fatigue that will not persist.

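### The primary hypothesis is framed as a >1 SD change from baseline and the named covariates omit the baseline score of the outcome test; if tested as written, power is lost at the same sample size

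*Protocol*

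**What the plan says.** The primary hypothesis in section 1(b) is that Veterans on active rTMS "will show improvement of > 1 SD on performance between baseline and post-treatment" on at least one of three tests: Trail Making Test part B, D-KEFS Verbal Fluency or D-KEFS Color-Word Interference, compared with sham. It gives an outcome and a threshold but no test or model. It does not say whether >1 SD is a cut applied to each participant or a difference in mean change.

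Covariates are named in section 9(a), in the discussion of procedure risks, as an aside about why cognitive problems persist: "depression and PTSD, chronic pain, sleep apnea (all will be) used as covariates in our analysis". The list has no time point and is not described as complete.

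Secondary hypothesis 3 brings in some baseline information, but as effect modifiers: "Moderators of Response. Age, severity of symptoms at baseline, type of comorbidity", and others. It does not name the baseline test score.

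Section 2(a) places the cognitive tests, including the main outcome measure, at baseline, post-treatment and 6 months, so the baseline score is already collected.

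On size, section 8(a) says "100 participants are expected to be enrolled", while sections 8(g) and 9(d) work with 40. No power calculation is given.

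**The concern.** The three tests give timed or counted scores. Reading such a score as change from baseline against a 1 SD mark can cost precision in two ways.

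- **The cut.** If each participant is classed as improved or not, the size of the change on either side of 1 SD is discarded.
- **The unadjusted change.** If mean change is compared without the baseline score in the model, the comparison is noisier than a baseline-adjusted one whenever the baseline-to-post correlation is below 1.

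The protocol does name covariates, and the baseline value of the outcome, usually the strongest available predictor of the post-treatment value, is not one of them. In a pilot that may stop at 40 participants, chance imbalance at baseline is not negligible, and precision that can be had from data already collected is worth having.

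**Working it through.** The protocol has no power figure to reproduce. What follows is an illustration, and its assumptions are marked.

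**Inputs from the protocol:** two arms, active and sham (section 2(a)); total 40 (sections 8(g), 9(d)) or 100 (section 8(a)); threshold 1 SD (section 1(b)).

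**Assumed:** 1:1 allocation; two-sided 5%; normal scores with SD 1 at both visits; one test; practice gain of 0.3 SD in both arms; true effect of 0.7 SD at 20 per arm and 0.5 SD at 50 per arm; baseline-to-post correlation ρ of 0.6, 0.7 or 0.8.

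**Step 1. Variance.** Raw change has variance 2(1−ρ). The baseline-adjusted score has residual variance 1−ρ². Their ratio is (1+ρ)/2.

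| ρ | Raw change | Adjusted | Reduction |
|---|---|---|---|
| 0.6 | 0.80 | 0.64 | 20% |
| 0.7 | 0.60 | 0.51 | 15% |
| 0.8 | 0.40 | 0.36 | 10% |

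**Step 2. Responder proportions at 0.7 SD.** In the active arm the mean change is 0.3 + 0.7 = 1.0, exactly the cut, so 50% respond. In the sham arm the proportion is 1 − Φ((1 − 0.3)/√(2(1−ρ))), which is 21.7, 18.3 and 13.4% for the three correlations.

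**Step 3. Power** (simulation; Fisher's exact test for responders, t-test for raw change, ANCOVA for the adjusted score).

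| Setting | ρ | >1 SD responders | Raw change | Baseline-adjusted |
|---|---|---|---|---|
| 20 per arm, 0.7 SD | 0.6 | 35% | 66% | 75% |
| | 0.7 | 46% | 79% | 85% |
| | 0.8 | 63% | 93% | 94% |
| 50 per arm, 0.5 SD | 0.6 | 48% | 79% | 87% |
| | 0.7 | 58% | 89% | 94% |
| | 0.8 | 75% | 97% | 98% |

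An exact calculation from the proportions in step 2 and the noncentral t distribution agrees with these to within about 2 points.

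**Step 4. Splitting the loss at 20 per arm.** From responders to raw change: 66 − 35 = 31, 79 − 46 = 33 and 93 − 63 = 30 points. From raw change to adjusted: 75 − 66 = 9, 85 − 79 = 6 and 94 − 93 = 1 points. The cut accounts for most of the loss.

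**Step 5. Dependence on baseline.** With 20 per arm, the between-arm baseline difference has SD √(2/20) = 0.32. At ρ = 0.7, a sham participant who starts 1 SD below the mean has expected change 0.3 + 0.3 = 0.6 and residual SD √0.51 = 0.714. The chance of passing the cut is 1 − Φ(0.4/0.714) = 29%. One who starts 1 SD above the mean has expected change 0.3 − 0.3 = 0, and the chance is 1 − Φ(1/0.714) = 8%. Whether a participant counts as improved therefore depends partly on where they started.

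**The case against.** The strongest reply is that the protocol fixes no primary model. Section 1(b) is a hypothesis, section 9(a) is an aside, and the covariate set of a primary model is commonly left to the SAP. A change score can also carry baseline as a covariate: in a simulated 40-participant data set the treatment t-statistic was 4.298 whether the adjusted outcome was the change or the post-treatment score. All of this stands. A reader might infer that the baseline score will not be adjusted for. The protocol does not say so; it says only which covariates will be used, and baseline is not on that list.

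Baseline severity does appear in secondary hypothesis 3. That shows baseline status was considered, but as a moderator in a secondary question, and it does not put the test score in the primary comparison.

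The stated rule is success on any one of three tests, so a one-test responder figure is not the power of that rule. This is fair. With an assumed correlation of 0.5 between tests and the effect present on all three, the any-of-three responder comparison at 20 per arm has power of about 45, 58 and 77%. That is still below the baseline-adjusted comparison on a single test (75, 85 and 94%).

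A reader might also infer that post-treatment depression, PTSD or pain scores will be entered as covariates. The questionnaires are repeated at follow-up ("Interviews, Self-Report Questionnaires (same as above"), and section 3(a) reports that rTMS is in use for pain, depression and PTSD, so such values could carry part of the treatment effect. Nothing in the protocol says they will be entered, however, and the same conditions appear as moderators, which normally implies pre-treatment values. This is a reason to state the time point and is not evidence of an error.

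**Conclusion.** The point holds in a conditional form. The protocol states its primary result as a >1 SD change from baseline and names covariates that do not include the baseline score of the outcome test. Under either reading of the threshold, a baseline-adjusted comparison of the same data is more efficient. If >1 SD is used as a responder cut, power at 20 per arm and 0.7 SD falls from 75–94% to 35–63%. If mean change is compared without adjustment, the loss is only about 1 to 9 points and shrinks as the correlation rises. These sizes rest on the assumed allocation, effect, practice gain and correlation, none of which the protocol gives. The document does not show that baseline adjustment has been ruled out.

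**What to change.** - **Section 1(b):** state that the arms are compared on the post-treatment score (or, equivalently, the change score) of each primary test, adjusted for the baseline score of that same test. Report the proportion improving by >1 SD in each arm beside it as a supporting description.
- **Section 9(a):** state that depression, PTSD, chronic pain and sleep apnea enter as baseline values.
- If an SAP exists, check whether it already says this, and align the two documents.

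The cost is wording in two sections and no new data. The small downside is that the headline becomes an adjusted mean difference, which is less immediate than a proportion improved. How the three tests are combined is a separate question that this change does not settle.

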**2. Study Procedures**

- a) **Please SUMMARIZE the research procedures, screening through closeout, which the human subject will undergo. Refer to sections in the protocol attached in section 16, BUT do not copy the clinical protocol. Be clear on what is to be done for research and what is part of standard of care.**

List of Procedures for the rTMS protocol:

Screening Measures:

- Telephone screening call: 1 hr
- Consenting and on-site screening: approx. 6 hrs
- Physical exam, medical history
- Medication review
- Interviews, self-report questionnaires  
Clinical TBI Evaluation
- Blood (60 cc), urine, and breath tests
- Determination of TMS motor threshold (markings on the cap will be marked with "MT" for motor threshold and "Tx" for treatment site.
- Eligibility determination
- Randomization to active or sham treatment

Baseline measures: approx. 8 hrs

- Interviews, self-report questionnaires, tasks (pain, fatigue, sleep, malingering, depression, PTSD, TBI, suicide, cognition);
- Cognitive testing (including main outcome measure for executive function) and webneuro computerized testing
- Neuroimaging: Diffusion Tensor Imaging (DTI), functional MRI (fMRI); structural MRI
- If indicated, and prior to MRI scan, an MRI X-ray screen will be performed if there is suspicion that participant may have metal in their body
- Pure Tone Audiometry

Intervention Measures:

- rTMS or sham treatment: up to 3 treatments a day for up to 5 days/week, 2-6 weeks = 20 sessions. Each session lasting 30-60 minutes in length. Depending on schedule, and at the physician's discretion, up to three rTMS sessions can be scheduled per day with a one hour interval between sessions, shortening treatment duration to 1.5 weeks.
- TMS motor threshold determination prior to the first treatment and every 5th day of treatment thereafter (at least weekly).
- Random breathalyzer and urine tests will be administered during the intervention phase to screen for drug and alcohol use; depending on results, participant may not be allowed to receive

**Title :** Repetitive Transcranial Magnetic Stimulation to Improve Cognitive Function in TBI  
**Approval Period:** 12/11/2018 - 02/13/2019

additional rTMS treatment for safety reasons

- Blood samples (60 cc) will be taken every 10 rTMS

treatment

for processing of BDNF from blood plasma.

- Headache and Pain self report will be recorded before and after every treatment session.

Follow-up (post treatment and 6 months): approx. 8.5 hrs

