- f) **State the number, if any, of participants who are healthy volunteers. Provide rationale for the inclusion of healthy volunteers in this study. Specify any risks to which participants may possibly be exposed. Specify the measures being taken to minimize the risks and the chance of harm to the volunteers and the additional safeguards that have been included in the protocol to protect their rights and welfare.**

Participants should all be in fair physical health though may be cognitively impaired as seen in the chronic symptoms of mild/moderate TBI (note we have removed the 1 SD or more below the mean score on Trail Making Test B (TMT B) criteria from our inclusion criteria). All procedures are considered low risk or standard of care.

- g) **How will you identify participants for recruitment? (E.g., by: chart review; referral from treating physician; response to ad). Attach recruitment materials in Section #16 (Attachments). All Final or revised recruitment materials, flyers, etc. must be submitted to the IRB for review and approval before use. You may not contact potential participants prior to IRB approval. See Advertisements: Appropriate Language for Recruitment Material.**

Based on the team established, we will recruit from: War Related Illness and Injury study Center (WRIISC) at VAPA (one of the three in the nation tasked to address complex problems faced by Veterans of the recent wars; PI: [name], PhD, Deputy Director Research), Polytrauma VAPA (Co-I: [name]; one of the 5 polytrauma network sites the country and a participating DVBIC site), Memory clinics at VAPA as well as from the surrounding VA clinics. Letters will be sent to patients and providers with information about the study, and a pre-paid response postcard. Phone calls will be made to these Veterans as followup within two weeks. Flyers will be posted in relevant clinic settings and on the Stanford University Marguerite Shuttle, and study information will be advertised on social media, including facebook. (We plan to recruit an average of 2.2 patients/month to meet our target enrollment of 40 participants in 18 months).

- h) **Inclusion and Exclusion Criteria.**

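### The primary hypothesis can be met on any one of three tests and lacks its comparison with sham, while other sections point to a single primary outcome

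*Protocol*

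**What the plan says.** Four places in the protocol bear on the primary outcome.

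- **Section 1, Primary Hypothesis.** Patients on active rTMS "will show improvement of > 1 SD on performance between baseline and post-treatment" and may do so "on any one of the following: the Trail Making Test part B, D-KEFS Verbal Fluency and/or D-KEFS Color-Word Interference Test". The sentence ends with a than-clause naming the sham group, but no word such as greater or more often comes before it.
- **Section 1(b), background on executive function.** A parenthesis reads "Trail Making Test (TMT: primary outcome measure". It gives no part (A or B), states no decision rule, and attaches the label to no other test.
- **Section 2(a), Study Procedures.** The baseline list has "Cognitive testing (including main outcome measure for executive function" and the follow-up list has "Cognitive testing including executive function main", continuing to the words for outcome measure in the singular. Neither names the test.
- **Section 1, Secondary Hypotheses, item 1.** The 6-month hypothesis uses "executive function improvement" without defining it, so it depends on whatever the primary rule is.

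The only other 1 SD in the protocol is in Section 8(f): "we have removed the 1 SD or more below the mean score on Trail Making Test B (TMT B) criteria". That is a distance below a mean in a deleted entry criterion, not a change from baseline, so it does not help to read the hypothesis.

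**The concern.** There are two linked problems.

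1. **Which outcome.** The hypothesis allows three routes to success. The background label and the singular wording in the procedures fit one outcome better. If only verbal fluency or only colour-word interference improves, the trial succeeds under the hypothesis as written and does not if the Trail Making Test is the primary outcome. The same data would support opposite primary conclusions.
2. **Which comparison.** Without its comparative, the sentence can mean that more active than sham patients gain over 1 SD, or that the arms differ by more than 1 SD. These are different estimands with different chances of success.

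Until one rule is written down, the documents shown do not fix what would count as a positive trial.

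**Working it through.** The protocol gives no alpha, power, allocation ratio or test reliability, so there is no figure of its own to reproduce. What follows only illustrates size.

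**Inputs.** Totals of 100 (Section 8(a): "100 participants are expected to be enrolled") and 40 (Section 9(d)) give 50 or 20 per arm if allocation is equal, which is assumed. The conflict between those totals is a separate matter. Also assumed: two-sided 5%, counting only results that favour rTMS; retest correlation r = 0.7; correlation between tests 0.3; practice gain 0.3 SD in both arms; SD taken as the baseline SD. Results are written as 20/50 per arm.

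**Responder reading.** A patient responds if any of the three changes exceeds 1.
- SD of change = √(2(1 − 0.7)) = 0.775.
- Sham patient, one test: P(change > 1) = 1 − Φ((1 − 0.3)/0.775) = 1 − Φ(0.904) ≈ 18%.
- Any of three, from the trivariate normal: sham 40.1%. Active: 53.6% if one test gains 0.5 SD, 70.3% if all three gain 0.5, 71.6% if one gains 1, 90.8% if all gain 1.
- Success is a pooled z test of the two proportions, with power by exact binomial enumeration.

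**Between-arm reading.** Success is an observed difference in mean change above 1 on any of the three tests.
- SE = √(2(1 − 0.7) × 2/n) = √(1.2/20) = 0.245, or √(1.2/50) = 0.155.
- One test with a true gain of 0.5: 1 − Φ(0.5/0.245) ≈ 2.1%, or 1 − Φ(0.5/0.155) ≈ 0.06%.
- At a true gain of exactly 1, one test crosses the threshold half the time.

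**Trail Making Test B alone.** Post-treatment score adjusted for baseline.
- SE = √((1 − 0.7²) × 2/n) = √(1.02/20) = 0.226, or √(1.02/50) = 0.143.
- For a true 0.5 the noncentral t gives 58%/93%; for a true 1, 99%/>99.9%.
- With no effect on this test, a result favouring rTMS occurs in 2.5%.

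**Chance of primary success**

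| True gain | Any of three, responder | Any of three, between-arm | TMT-B alone |
|---|---|---|---|
| One D-KEFS test, 0.5 SD | 12%/29% | 2.1%/0.06% | 2.5%/2.5% |
| One D-KEFS test, 1 SD | 51%/91% | 50%/50% | 2.5%/2.5% |
| All three, 0.5 SD | 47%/88% | 6%/0.2% | 58%/93% |
| All three, 1 SD | 96%/>99.9% | 80%/80% | 99%/>99.9% |

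**Trials in which any-of-three and TMT-B alone disagree** (simulated, 20,000 trials per scenario; simulation error at most 1.96 × √(0.25/20,000) ≈ 0.7 percentage points)

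| True gain | Responder reading | Between-arm reading |
|---|---|---|
| One D-KEFS test, 0.5 SD | 13%/28% | 4%/3% |
| One D-KEFS test, 1 SD | 49%/88% | 48%/48% |
| All three, 0.5 SD | 36%/13% | 52%/93% |

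The 4%/3% is made up largely of chance successes on TMT-B, because the between-arm threshold is almost never crossed at 0.5 SD. The last row reflects mainly the 1 SD threshold, not which test is primary, so it should not be used to size the conflict over the outcome.

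**The case against.** **The label is weak evidence.** It is a parenthesis in a literature paragraph and does not say sole or only. TMT-B is itself one of the three tests, so the label could name a primary measure among several, and Section 2(a) names no test. This stands: a reader might infer that the protocol makes the Trail Making Test its only primary outcome, and the text does not go that far. It remains the only test called primary, the procedures use the singular, and nothing shown explains how this fits an any-of-three rule.

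**Other documents may settle it.** Section 16 lists a grant and a cognitive test battery, neither shown; registration is planned; an analysis plan may exist. It follows that one cannot say the rule will be picked after the results are seen. An analysis plan may also choose the SD and any multiplicity method, so neither the unnamed SD nor an inflated error rate is a finding here. A reader might compute a family-wise error for three unadjusted tests, but the protocol does not say that they would go unadjusted.

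**A within-arm reading is possible.** A reader might take the sentence to mean a mean gain above 1 SD in the active arm alone. The reference to the sham group argues against that, and it is left out.

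**It is a pilot.** True, and this lowers the severity. The protocol still states a primary efficacy hypothesis against sham.

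**Conclusion.** The point holds in a limited form. The protocol does not give one consistent account of its primary outcome, and the hypothesis sentence does not complete its comparison with sham. This is an unreconciled inconsistency plus an incomplete criterion, not proof of two flatly incompatible primary outcomes.

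The size depends on the true effect and on the reading. The conflict over the outcome is small under the between-arm reading at 0.5 SD and large under either reading at 1 SD. The gap between the two readings runs the other way: wide at 0.5 SD and much narrower at 1 SD. All percentages rest on the assumed reliability, correlation, practice gain and equal allocation; none contradicts a figure in the protocol. This should be fixed, but in a pilot it is not a fault that must stop the trial.

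**What to change.** Before unblinding, state one primary decision rule, complete the active-versus-sham comparison in the Primary Hypothesis, and make Section 1(b), the Primary Hypothesis and both lists in Section 2(a) agree. Use the same definition for the improvement named in Secondary Hypothesis 1. Either route resolves it:

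- **(a) One test.** TMT-B is the single primary outcome and the two D-KEFS tests are secondary. A benefit confined to a D-KEFS test then no longer counts as primary success.
- **(b) Three tests.** All three are primary, with Holm at an overall two-sided 5%, or combined in one any-of-three responder outcome compared between arms. The label in Section 1(b) and the singular in Section 2(a) are corrected.

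Under (b) with Holm and baseline-adjusted scores, power at 0.5 SD is about 40%/86% if only one test gains. That compares with 58%/93% for TMT-B alone when TMT-B is the test that gains. If all three gain, Holm reaches about 69%/98%. The responder version gives 12%/29% if one test gains 0.5 SD and 47%/88% if all three do.

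The administrative cost is an IRB modification, plus a matching registry entry if the trial has been registered. No new data are needed.
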